3.4.2 Vaccination Administration

Vaccine dosing will begin with Cohort 1 (10 μ g mRNA-1893 or placebo), followed sequentially by Cohort 2 (30 μ g mRNA-1893 or placebo), Cohort 3 (100 μ g mRNA-1893 or placebo), and Cohort 4 (250 μ g mRNA-1893 or placebo).

The vaccine will be administered as an IM injection into the deltoid muscle on a 2-dose vaccination schedule at Day 1 and Day 29 (e.g., at least a 28-day interval between dosing).

In each cohort, the initial 5 participants enrolled will be flavivirus seronegative and randomly assigned to vaccine or placebo (4:1 mRNA-1893 to placebo) before the remaining participants (n=25, 20 seronegative and 5 seropositive) are enrolled in the cohort.

Each vaccination will contain 0.5 mL of 10, 30, 100, or 250 µg mRNA-1893 or 0.5 mL of placebo. Preferably, the second dose of vaccine should be administered in the same arm used for the first dose.

The vaccine will be prepared as detailed in the Pharmacy Manual. Unblinded pharmacy personnel, who will not participate in any other aspect of the study, will perform vaccine accountability, dose preparation, and vaccine administration. The investigator or designee will be responsible for oversight of the administration of vaccine according to the procedures stipulated in this study protocol and the Pharmacy Manual.

At each visit when vaccines are administered, participants will be monitored for 60 minutes after vaccine administration; assessments will include vital sign measurements and monitoring for local or systemic reactions (Schedule of Events, Table 5).

Eligibility for subsequent study vaccination is determined by following the criteria outlined in Section 3.4.2.3.

The clinic will be appropriately staffed, will be trained on emergency resuscitation, and will have stocked available rescue medications (such as epinephrine, steroids, antihistamines, and IV fluids) should any severe reaction (e.g., anaphylaxis or urticaria) occur that requires immediate intervention.

Details regarding safety oversight of within-cohort dosing and dose escalation are provided in Section 3.4.2.1. The rules for pausing dosing are provided in Section 3.4.2.2.

3.4.2.1 Dose Escalation

For each dose cohort (Cohorts 1 through 4), Safety Oversight will be performed 7 days after the first 5 participants (all seronegative) are randomly assigned and receive their first study vaccination (Day 1) before randomly assigning the remaining participants in the cohort. Once safety is confirmed (i.e., no safety concerns and pause rules as defined in Section 3.4.2.2 have not been met), the study medical monitor will authorize the random assignment of the remaining 25 participants in the cohort. Seven days after all 30 participants in the cohort have received the first study vaccination, a blinded IST that is not directly involved in the day-to-day activities of the study, will review all available safety data for the currently dosed cohort and any cumulative safety data of all cohorts as the trial advances to determine the

acceptability to escalate to the next mRNA-1893 dose level. The 30 participants in the first cohort will continue to receive their second study vaccine dose on Day 29 (+14 days).

Oversight of safety will be performed in a blinded manner by the contract research organization's (CRO's) medical monitor, the Sponsor's medical monitor, and the individual site principal investigators throughout the study for all participants.

The blinded IST will oversee the safety of the trial and will review safety data to ensure adherence to the protocol, monitor safety laboratory test results and reactogenicity, and they may request input from the SMC should the study meet pause rules (Section 3.4.2.2) or for any other study events that could potentially affect participant safety. The IST will approve escalation to the next higher dosing cohort after review of blinded safety data of the currently dosed cohort through 7 days following the first vaccination and any cumulative safety data of all cohorts as the trial advances.

The IST is composed of 3 Sponsor clinicians who are not directly involved in the day-to-day conduct of the study and who are the voting members for decision for dose escalation. Additionally, the investigator, the CRO medical monitor, and the Sponsor medical lead will be nonvoting extended members. A Biomedical Advanced Research and Development Authority representative may also join these meetings as an observer. Details regarding composition, responsibilities, and procedures of the IST are presented in the IST charter.

An independent, unblinded SMC will be consulted at the discretion of the IST or if a pause rule is met (Section 3.4.2.2). The SMC will review all available safety data to adjudicate any potential study pauses and make recommendations on further study conduct, including requesting additional information, recommending stopping the study, recommending changes to study conduct and/or the protocol, or recommending additional operational considerations due to safety issues that arise during the study.

The SMC will be comprised of external independent consultants with relevant expertise. Details regarding composition, responsibilities, and procedures of the SMC are presented in the SMC charter.

3.4.2.2 Pause Rules

Study pause rules will be continuously monitored during all phases of the study by the investigators, study medical monitor, Sponsor medical lead, IST, and SMC (as warranted). If the investigator, study medical monitor, Sponsor medical lead, IST, or SMC request that the study be paused due to a safety concern, further study vaccine administration in the affected cohort and at higher dose levels will be suspended, but all other planned procedures relating to safety, reactogenicity, and immunogenicity assessments will continue as described in the protocol.

The occurrence of any of the events listed in Table 2, regardless of dosing group, will result in immediate suspension of dosing and enrollment in the cohort. An unscheduled meeting of the SMC will be convened to assess specific data concerns and to make recommendations.

The Sponsor will notify the Center for Biologics Evaluation and Research within 48 hours in the event of a study pause.

Table 2: Pause Rules Based on the Occurrence of a Single Adverse Event and Adjudicated by the SMC

Pause Rule	Adverse Event	Number of Participants per Dose Cohort
1	Any serious adverse event that cannot be reasonably attributed to a cause other than vaccination	≥ 1
2	Any Grade 4 adverse event that cannot be reasonably attributed to a cause other than vaccination	≥ 1
3	Any systemic immediate hypersensitivity reaction within 60 minutes after the study vaccination	≥ 1

Abbreviation: SMC = Safety Monitoring Committee.

Table 3 summarizes safety events that will pause study dosing based on defined threshold levels, which are aggregate incidences relative to the number of exposed participants within a dosing group. An unblinded statistician may be consulted to determine if a pause rule has been met.

Table 3: Pause Rules Based on the Occurrence of Adverse Events in a Proportion of Participants

Pause Rule	Adverse Event	Number of Participants per Dose Cohort ^a	
4	Any Grade 3 solicited local adverse event lasting more than 24 hours in an mRNA-1893 cohort ^b within the 7-day (Days 1-8) post-vaccination period	≥ 20% and ≥ 2 participants/group	
5	Any Grade 3 solicited general adverse event lasting more than 24 hours in an mRNA-1893 cohort ^b that cannot be reasonably attributed to a cause other than vaccination, within the 7-day (Days 1-8) post-vaccination period	\geq 20% and \geq 2 participants/group	
6	Any ≥ Grade 3 unsolicited adverse event in an mRNA-1893 cohort ^b that cannot be reasonably attributed to a cause other than vaccination OR Any ≥ Grade 3 laboratory abnormality ^c in an mRNA-1893 cohort ^b that cannot reasonably be attributed to a cause other than vaccination	≥ 20% and ≥ 2 participants/group	

^a For the first 5 participants in each dose level cohort, the pause rule will be considered met if 2 of the first 5 participants experience the same event regardless of dosing group.

If a pause is triggered in the study, each participant's clinic visits will continue until the next scheduled vaccination visit. If a pause affects a participant's vaccination visit, the window for that participant's vaccination visit will be suspended until the pause is lifted and vaccination can resume. Once the pause is lifted at a site, vaccination should be reinstated as soon as possible. Clinic visits should thereafter (Day 36 [+3 days], Day 57 [-7/+14 days], Month 7 [± 14 days], and Month 13 [± 14 days]) be scheduled as if participants had received their second vaccination within the 28 (+14) day window. The Dose 2 window may be extended to 28 (+14) days at the discretion of the principal investigator and with approval of the study medical monitor on a case by case basis for participants whose window is affected by a study pause.

b The rate of adverse events and laboratory abnormalities will be computed based on the number of exposed participants who have provided safety data (i.e., have completed a post-dosing visit for assessment of safety).

Grading of laboratory parameters will be based on the US Food and Drug Administration Guidance for Industry "Toxicity grading scale for healthy adult and adolescent volunteers enrolled in preventive vaccine clinical trials" (DHHS 2007).

If a pause is prolonged such that the second vaccination takes place outside the 28 (+14) day window, the Sponsor has the option to add additional participants in a dosing cohort to achieve the original number of participants planned for dosing within the 28 (+14) day window. If a participant is in the Screening Phase for more than 28 days as the result of a pause, the participant may be rescreened for study eligibility (and will receive a new screening number) as long as the participant continues to provide consent to participate in the study.

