cohort and any cumulative safety data of all cohorts as the trial advances to determine the acceptability to escalate to the next mRNA-1893 dose level. The 30 participants in the first cohort will continue to receive their second study vaccine dose on Day 29 (+14 days).

The blinded IST will oversee the safety of the trial and will review safety data to ensure adherence to the protocol, will monitor safety laboratory test results and reactogenicity, and may request input from the SMC should the study meet pause rules or for any other study events that could potentially affect participant safety. The IST will approve escalation to the next higher dosing cohort after review of blinded safety data of the currently dosed cohort through 7 days after the first vaccination and any cumulative safety data of all cohorts as the trial advances.

A diagram of the dosing schema by cohort is shown in Figure 1.

[figure not shown]

Figure 1: Dosing Schema by Cohort

Abbreviations: IST = internal safety team; S- = flavivirus seronegative; S+ = flavivirus seropositive.

Note: For each dose cohort (Cohorts 1 through 4), Safety Oversight will be performed 7 days after the first 5 participants (all flavivirus-seronegative) are randomly assigned and receive their first study vaccination (Day 1) before randomly assigning the remaining 25 participants in the cohort. Seven days after all 30 participants in the cohort have received the first study vaccination and review of all available safety data has been performed (ie, no safety concerns and pause rules have not been met), the IST will determine the acceptability to escalate to the next mRNA-1893 dose level.

During the Vaccination Phase, participants will be instructed to contact the Investigator immediately should they develop any untoward signs or symptoms or any medical occurrence that leads to an unplanned visit to a health care practitioner, hospitalization, or an emergency room visit. In case of MAAEs, if the participant presents with clinical symptoms

that may suggest a dengue infection, a blood sample should be collected for testing of dengue infection. In addition, participants will be instructed to contact the site within 24 hours, in the event of any severe Grade 3 local and systemic reactogenicity AE (solicited AEs; Section 3.5.6) or any episode of rash within 6 days after study vaccination.

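### Read literally, the automatic Table 2 pause stops only the affected cohort, so a higher dose level already open is not held unless a named party asks for it

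*Protocol*

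**What the plan says.** Protocol section 3.4.2.2 (Pause Rules) describes three kinds of pause.

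- **Requested pause (opening paragraph).** If the investigator, study medical monitor, Sponsor medical lead, IST or SMC asks for a pause over a safety concern, "further study vaccine administration in the affected cohort and at higher dose levels will be suspended".
- **Automatic pause, Table 2.** One qualifying event in either arm "will result in immediate suspension of dosing and enrollment in the cohort". The next sentence adds: "An unscheduled meeting of the SMC will be convened to assess specific data concerns and to make recommendations". The triggers are an SAE or a Grade 4 event with no reasonable cause other than vaccination, and a systemic immediate hypersensitivity reaction within 60 minutes.
- **Threshold pause, Table 3.** The introduction refers to "safety events that will pause study dosing based on defined threshold levels" and does not name the cohorts that stop.

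Section 3.4.2.1 (Dose Escalation) sets the timing. The IST approves the next level after "review of blinded safety data of the currently dosed cohort through 7 days following the first vaccination", together with cumulative data. First-cohort participants "will continue to receive their second study vaccine dose on Day 29 (+14 days"), and the Schedule of Events gives the Day 29 visit the same +14 window.

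Two gates depend on the pause rules. Within a cohort, the remaining 25 participants are released only if there are "no safety concerns and pause rules as defined in Section 3.4.2.2 have not been met". The Figure 1 note in section 3.1 ties escalation to a review finding "no safety concerns and pause rules have not been met".

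**The concern.** The scopes appear to be in the wrong order. A discretionary request holds the higher doses. The gravest predefined triggers, which fire without anyone's discretion, are worded to hold only the cohort where the event happened. In a first-in-human dose escalation, a vaccine-attributable SAE at a low dose bears directly on the safety of the doses above it.

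This matters only if a higher level can be open when a lower-dose event occurs. If it can, the protocol leaves sites to work out whether injections already authorised at the higher level should stop at once or wait for a request. Different sites could read the scope differently.

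**Working it through.** The plan gives no figure on this point. The check is a comparison of wording followed by day arithmetic.

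**Step 1. Scope, side by side (section 3.4.2.2).**

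| Pause | What starts it | Stated scope | Higher levels named? |
|---|---|---|---|
| Requested | A named party's request | Vaccination in the affected cohort and above | Yes |
| Table 2 | The event itself | Dosing and enrolment in the cohort | No |
| Table 3 | A threshold being met | Study dosing, cohorts not stated | Unclear |

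The Table 2 sentence has its own trigger, states its own consequence, adds an enrolment stop that the opening paragraph lacks, and does not refer back to that paragraph. Its application to either arm widens who can trigger the pause, not what stops. No sentence in the protocol or SAP extends it to higher doses.

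**Step 2. Can a higher level already be open?** Count from the dose 1 of the last participant dosed in the lower cohort (Day 1).

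- Earliest escalation: 1 + 7 = Day 8, assuming the IST approves the same day.
- Dose 2 window: Day 29 to 29 + 14 = Day 43.
- Lead of the opening over that dose 2: 29 − 8 = 21 days, to 43 − 8 = 35 days. Each day of IST delay removes one day.

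For the five sentinels on the fastest schedule, dose 1 is at day 0, the other 25 are dosed at day 7, and escalation is at day 7 + 7 = 14. Sentinel dose 2 falls at day 28 to 42, so the lead is 28 − 14 = 14 to 42 − 14 = 28 days. Slower enrolment shortens this second lead but not the first.

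The pause rules are monitored in all study phases. A Table 2 event after lower-cohort dose 2, or a late event after dose 1, can therefore occur with the next level open. This applies to Cohorts 1 to 3, since nothing lies above 250 µg.

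**Step 3. What do the gates cover?** They block release of the 25 and the opening of a new level. Neither recalls injections already authorised at an open level.

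**Step 4. How many doses?** This would need the time from the event to a wider hold and the enrolment rate at the higher level. The documents give neither, so no count is offered.

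**The case against.** The best counter-argument is that section 3.4.2.2 should be read as a whole. Its opening paragraph names the parties who monitor the pause rules, and the same parties' request brings the wider suspension. Table 2 may simply add immediacy and an enrolment stop to that general scope. Other wording leans the same way: section 3.4.2.1 speaks of the study meeting pause rules and of the SMC adjudicating study pauses, while section 3.4.2.2 speaks of a pause triggered in the study and of notifying the regulator of a study pause. This reading is reasonable. It does not settle the matter, because none of these sentences says which cohorts stop, and section 3.4.2.2 also speaks of lifting a pause at a site.

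Second, the people who recognise a Table 2 event are largely those entitled to request the wider hold, so both could start together. SAEs reach the Sponsor within 24 hours (section 3.5.7.3), participants are observed for 60 minutes after injection, and the SMC meeting is mandatory. This stands and makes the gap small. What remains is that the wider hold is discretionary, and these documents set no deadline for the SMC meeting.

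Third, a local automatic stop with a wider hold on request may be deliberate, since one event in a low-dose placebo recipient would otherwise halt every open higher cohort. That is defensible, but the protocol does not say it was intended. The IST and SMC charters, which hold the committees' procedures, were not available and may state the scope.

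**Conclusion.** The point holds as a gap in wording with a safety consequence. The automatic Table 2 pause is narrower on its face than a requested pause, the Table 3 scope is unstated, and the schedule makes it possible for a higher level to be open when a lower-dose event occurs. The measurable part is the lead of 21 to 35 days for the last lower-cohort participant, on same-day IST approval. That is an overlap of dose levels, not a duration of exposure.

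Two stronger inferences are not supported. A reader might conclude that higher-dose injections will carry on until the SMC reports. The documents show only that the Table 2 sentence does not itself hold them; any of five parties can do so at once. A reader might also conclude that escalation to an unopened level could proceed after a Table 2 event, but the gates prevent that while a pause rule is met.

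The change is a cheap improvement and worth making. The conclusion rests on the protocol and SAP alone.

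**What to change.** Reword the Table 2 sentence so that the immediate stop covers first doses, second doses and enrolment, in the affected cohort and at every higher dose level, until the SMC has reviewed the event. In the text introducing Table 3, state at least the same scope, and keep it study-wide if that was meant. If a cohort-only automatic stop is intended, say so expressly and set a time limit for the SMC meeting.

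The text change is one clause in each place. The operational cost is a temporary hold of open higher cohorts, including when the event proves to be in a placebo recipient. A reader might expect a count of second doses lost to the visit window, but none can be given. Section 3.4.2.2 suspends an affected participant's vaccination window until the pause is lifted. It also lets the Sponsor add participants if a prolonged pause takes second doses outside the 28 (+14) day window.

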3 INVESTIGATIONAL PLAN

3.1 Study Design

This is a Phase 1, randomized, observer-blind, placebo-controlled, dose-ranging study to evaluate the safety, tolerability, and immunogenicity of Zika vaccine mRNA-1893 administered to healthy flavivirus-seropositive and seronegative adult participants (18 to 49 years of age, inclusive). A total of 120 participants (30 participants per cohort) will be enrolled into 1 of 4 mRNA-1893 dose cohorts (10, 30, 100, or 250 µg). Within each cohort, eligible participants will be randomly assigned to mRNA-1893 or placebo (4:1 mRNA-1893 to placebo) and administered the study vaccine as an IM injection on a 2-dose vaccination schedule, 28 days apart (Day 1 and Day 29). Participants will be stratified by baseline flavivirus serostatus (seropositive and seronegative).

The study will comprise a Screening Phase (up to 28 days), a Vaccination Phase (up to 57 days), and a Long-Term Follow-up Phase (up to 12 months after last vaccination) (Table 5). Participants will have approximately 8 clinic visits with an additional 13 safety telephone calls. Study duration will be approximately 13 months for each participant. Participants will provide written informed consent before any study-specific procedures are performed.

Study vaccine dosing will begin with Cohort 1 (10 µg mRNA-1893 or placebo), followed sequentially by Cohort 2 (30 µg mRNA-1893 or placebo), Cohort 3 (100 µg mRNA-1893 or placebo), and Cohort 4 (250 µg mRNA-1893 or placebo). Vaccine accountability, dose preparation, and vaccine administration will be performed by unblinded pharmacy personnel, who will not participate in any other aspects of the study. The remainder of the study staff and all participants will remain blinded to dosing assignment.

For each dose cohort (Cohort 1 through 4), Safety Oversight will be performed 7 days after the first 5 participants (all seronegative) are randomly assigned and receive the first study vaccination (Day 1). Once safety is confirmed, the remaining 25 participants in the dose level cohort will be randomly assigned to dosing. Seven days after all 30 participants in the cohort have received the first study vaccination, a blinded IST that is not directly involved in the day-to-day activities of the study, will review all available safety data for the currently dosed

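### Escalation depends on the Table 3 pause rules not being met, but no unblinded check of them is required beforehand; the Table 3 header and footnote b should also state the per-group denominator

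*Protocol*

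**What the plan says.** **Threshold.** Rules 4 to 6 in Table 3 pause dosing at 20% or more and at least 2 participants per group. The text above the table describes the thresholds as "aggregate incidences relative to the number of exposed participants within a dosing group". Footnote a adds a rule for the start of each cohort: a pause if "2 of the first 5 participants experience the same event regardless of dosing group".

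**Labels around the threshold.** The column header reads "Number of Participants per Dose Cohort". Row 4 counts events "lasting more than 24 hours in an mRNA-1893 cohort", and footnote b, attached to that phrase, says the rate is "computed based on the number of exposed participants who have provided safety data". Section 3.1 uses similar words for groups that include placebo: "120 participants (30 participants per cohort) will be enrolled into 1 of 4 mRNA-1893 dose cohorts".

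**Escalation.** The Figure 1 note in section 3.1 makes the decision to escalate follow a review in which no pause rule has been met. Section 3.4.2.1 gives that decision to a blinded IST, on data through 7 days after the first dose.

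**Unblinded evaluation.**
- Protocol 3.4.2.2: "An unblinded statistician may be consulted to determine if a pause rule has been met".
- Protocol 3.4.5: an unblinded statistician evaluates the Table 3 criteria as part of the analysis that follows completion of each dosing cohort. The interim analysis in 3.6.8 comes after Visit 9 (Day 57).
- SAP 5.4: assigns the same evaluation and gives it no separate time.
- Protocol 3.4.2.1: "An independent, unblinded SMC will be consulted at the discretion of the IST or if a pause rule is met".

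**The concern.** This is a first-in-human escalation from 10 to 250 µg, and the proportion rules protect the next cohort. A condition on escalation is useful only if the body that applies it can tell whether it holds. The first-5 rule can be applied blind, because it ignores dosing group. The proportion rule concerns vaccinees only, so a blinded total does not always settle it.

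Where the total does not settle it, the plan offers a discretionary consultation, an evaluation placed after cohort completion, and an SMC referral once a rule is met. The last does not help a team that cannot see whether the rule is met. As written, the study could move to the next dose with a rule met and nobody obliged to find out.

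The denominator labels are a smaller matter. Someone working from the table alone would not find in the header or footnote b the restriction that the text states.

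**Working it through.** **Inputs.** Each cohort has 30 participants, 24 on vaccine and 6 on placebo (Protocol Table 1). The threshold is at least 20% and at least 2 (Table 3). The documents give no event rates, so all rates below are assumed.

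**The plan's own figure.** The documents give no count or operating characteristics for the pause rule. The nearest figure is the chance of at least one AE among 24 vaccinees (Protocol 3.6.4): 1 - 0.90^24 = 0.920 and 1 - 0.95^24 = 0.708. These match the stated 92% and 70.8%, and they confirm 24 as the vaccinee group size.

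**Threshold as a count.** 0.20 × 24 = 4.8, so 5 vaccinees are needed (5/24 = 20.8%); 4/24 = 16.7% does not trigger. A denominator of all 30 would need 0.20 × 30 = 6, and 5/30 = 16.7% would not trigger. In a full cohort, the rule as the text states it is met while a count over all 30 is not only when there are 5 vaccinee and 0 placebo events.

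**What a blinded total can show.** Let V be vaccinee events, U placebo events (at most 6) and T = V + U. Then V lies between max(0, T - 6) and T.
- T ≤ 4: V cannot reach 5, so the rule is not met.
- T ≥ 11: V is at least 5, so the rule is met.
- T = 5 to 10: either is possible. The rule fails only if U ≥ T - 4, that is, at least 1 placebo event at T = 5, 2 at T = 6, 3 at T = 7 and all 6 at T = 10.

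**How often, and where the ambiguity lies.** V ~ Bin(24, p), U ~ Bin(6, q), full cohort, one event type, one look.

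| Vaccinee rate p | 10% | 20% | 25% |
|---|---|---|---|
| P(T = 5 to 10), q = 0 | 0.085 | 0.536 | 0.732 |
| P(T = 5 to 10), q = 5% | 0.127 | 0.590 | 0.758 |
| P(T = 5, rule not met), q = 5% | 0.037 | 0.050 | 0.033 |
| P(T = 6, rule not met), q = 5% | 0.004 | 0.006 | 0.004 |
| P(T = 7 to 10, rule not met), q = 5% | 0.0003 | 0.0005 | 0.0003 |
| P(T ≥ 5, rule not met), q = 5% | 0.042 | 0.057 | 0.037 |

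Example for row 3 at p = 20%: P(T = 5) = 0.194, and the rule is met there only at V = 5, U = 0, with probability 0.196 × 0.95^6 = 0.144. The difference is 0.050.

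With q = 0, every total of 5 or more is a true trigger. The first two rows therefore show how often assignments are formally needed, not how often a pause would be missed.

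**Workload of a required check at T ≥ 5.** P(T ≥ 5) is 0.016 at 5% in both arms; 0.085, 0.540 and 0.753 at p = 10%, 20% and 25% with q = 0; and 0.127, 0.597 and 0.791 with q = 5%. The last table row is the chance that a call proves unneeded. It is 0.010 at 5% in both arms.

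**The case against.** **The denominator is already settled.** The text, the per-group threshold cells, footnote a's need to waive dosing group for the first five, and the role given to an unblinded statistician all point to vaccinees. Table 2 carries the same column header, so it looks like a shared label. This stands. A reader might infer from the header that the operative trigger is 6 of 30, and might then calculate a chance of missed pauses. The documents do not support that: such a figure would apply only if staff set aside the governing text. What remains is an editorial alignment.

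**A check is available.** Pause rules are monitored continuously, the statistician may be consulted at any time, the SAP clause is compatible with on-demand use, and the IST can turn to the unblinded SMC. This also stands. A reader might infer that the plan contains no unblinded check before escalation, which would be too strong. The supportable statement is that none is required.

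**The ambiguity is narrow.** At a 5% placebo rate, a total of 7-10 with the rule not met has probability of at most 0.0005. That is correct, and it limits the practical doubt to totals of 5 and 6. It does not remove the gap, because nothing tells the IST to treat a total of 7 as a trigger either.

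**Other safeguards exist.** Escalation also requires no safety concerns. Several parties can request a pause without any threshold, and one unexplained serious or Grade 4 event pauses the cohort. These reduce the consequence, but none of them checks the proportion rule.

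**The charters are unseen.** They may contain the step, so its absence is shown only for the protocol and SAP.

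**Conclusion.** The point holds as a low-cost improvement to a safety procedure. The protocol sets the Table 3 threshold at 5 of 24 vaccinees in a full cohort, and the header and footnote b should say so. Escalation is conditional on that threshold not being reached, the deciding team is blinded, and neither document requires an unblinded check in time for the decision.

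A full-cohort blinded total of 5-10 formally leaves the condition unverified. At assumed vaccinee rates of 10% to 25% and placebo rates of 0 or 5%, that range has probability 0.085 to 0.758 for one event type at one look. Real doubt is mostly at 5 and slightly at 6. None of these figures is a probability that a pause would be missed, because that depends on whether the optional consultation is used.

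The conclusion assumes a 24:6 split, safety data from all 30 participants, and independent events at assumed rates. It would fall away in part if a charter already mandates the check.

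**What to change.** 1. In the Table 3 header and footnote b, define the denominator as exposed mRNA-1893 recipients at that dose level who have safety data. Leave the first-5 rule unchanged.
2. In Protocol 3.4.2.2 and 3.4.5 and SAP 5.4, require a step before any escalation decision. Whenever the blinded count for an event could meet the vaccinee threshold (5 in a full cohort), it goes to the existing unblinded statistician or SMC. Preferably only the SMC's recommendation returns to blinded staff.
3. If the IST or SMC charter already requires this, cite it in 3.4.2.2 instead.

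**Cost.** The change is wording in three sections and needs no new roles. Tallies could be frequent if reactogenicity is common, but unneeded calls have probability of at most about 0.06 per event type per look in the scenarios shown. There is a blinding cost: an answer of met at a total of exactly 5 reveals that all five are vaccinees. Routing through the SMC limits that disclosure.
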